**Table 4-2 Overall GCIG Criteria for Patients without Measurable Disease per RECIST at Baseline**

CA-125	Non-target Lesions	New Lesions	Overall GCIG Response
Response and Normalized (CR)	CR	No	CR
Response (PR)	Non-PD	No	PR
Normalized but no response	Non-CR/Non-PD	No	SD
Non-PR/non-PD	Non-PD	No	SD
PD	Any	Yes or No	PD
Any	PD	Yes or No	PD
Any	Any	Yes	PD

**Table 4-3 Overall GCIG Criteria for Patients with Measurable Disease per RECIST at Baseline**

Target Lesions	Non-target Lesions	New Lesions	CA-125 Response	Overall GCIG Response
CR	CR	No	Normal [1]	CR
CR	Non-CR/Non-PD	No	Not PD [2]	PR
CR	CR	No	PR	PR
CR	Not evaluable	No	PR but not normal	PR
PR	Non-PD or Not all evaluated	No	Not PD	PR
Not all evaluated	Non-PD	No	PR	PR
PD or New Lesion >28 days from CA-125 Response [3]			PR	PR
SD	Non-PD	No	PR	PR
SD	Non-PD or Not all evaluated	No	Not PR/ Not PD	SD
PD or New Lesion ≤28 days from CA-125 Response [3]			PR	PD
PD	Any	Yes or No	Any	PD
Any	PD	Yes or No	Any	PD
Any	Any	Yes	Any	PD
Any	Any	Yes or No	PD	PD

Note: See Table 4-1 for CA-125 response definitions.

[1] "Normal" includes both Normalized and CR.

[2] "Not PD" includes Normalized, CR, or PR.

[3] Patients who have CA-125 response that occurs more than 28 days from PD according to RECIST 1.1 are considered a PR, according to best response, but PD if the RECIST 1.1 PD is within 28 days of CA-125 response.

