Appendix 12: Evaluation of Response According to CA-125

(Modified from *Rustin, Vergote, Eisenhauer et al*)

A CA-125 response is defined as at least a 50% reduction in CA-125 levels from a pretreatment sample. The response must be confirmed and maintained for at least 28 days. Patients can be evaluated according to CA-125 only if they have a pretreatment sample that is at least twice the upper limit of the reference range and within 2 weeks before starting the treatment.

To calculate CA-125 responses accurately, the following rules apply:

- Intervening samples and the 28-day confirmatory sample must be less than or equal to (within an assay variability of 10%) the previous sample.
- Variations within the reference range of CA-125 levels will not interfere with the response definition.
- For each patient, the same assay method must be used, and the assay must be tested in a quality control scheme.
- Patients are not evaluable by CA-125 if they have received mouse antibodies (unless the assay used has been shown not to be influenced by human anti-mouse antibody) or if there has been medical and/or surgical interference with their peritoneum or pleura during the previous 28 days (e.g., paracentesis). If assessing therapy that includes 2 treatment modalities for relapse (e.g., surgery and chemotherapy), any CA-125 response results from both treatment modalities. CA-125 cannot distinguish between the effects of the 2 treatments

The date when the CA-125 level is first reduced by 50% is the date of the CA-125 response. To calculate response, an intent-to-treat analysis should be used that includes all patients with an initial CA-125 level of at least twice the upper limit of the reference range as eligible and evaluable. In addition, as a separate analysis, those patients who have a CA-125 response and whose CA-125 level falls to within the reference range can be classified as CA-125 complete responders.

In [Table 9 \(Appendix 13\)](#) and [Table 10 \(Appendix 14\)](#) where CA-125 is stated as normalized or normal, means within the reference range. Patients who have a fall of CA-125 to within the reference range but whose initial CA-125 was less than twice the upper limit of the reference range have not had a CA-125 response and cannot therefore be classified as a CA-125 complete responder.

Appendix 13: Evaluation of Best Overall Response in Patients Without Initial Measurable Disease and Who Are Evaluable by CA-125

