Table 9: Evaluation of Best Overall Response in Patients Without Initial Measurable Disease and Who Are Evaluable by CA-125

CA-125	Nontarget Lesions^a	New Lesions	Overall Serological Response	Best Response for this Category also Requires
Response and Normalized	CR	No	CR	Confirmed and maintained for at least 28 days
Response	Non-PD	No	PR	
Normalized but no response	Non-CR/Non-PD	No	SD	
Non-PR/non-PD	Non-PD	No	SD	
PD	Any	Yes or No	PD	
Any	PD ^b	Yes or No	PD	
Any	Any	Yes	PD	

^a Nontarget lesions include ascites and peritoneal thickening, which are not measurable according to RECIST.

^b Unequivocal progression in nontarget lesions maybe accepted as disease progression.

CR-complete response; PD-progressive disease; PR-partial response; SD-stable disease

Appendix 14: Best Overall Response in Patients with Measureable Disease and Who Are Also Evaluable by CA-125

Table 10: Best Overall Response in Patients with Measureable Disease and Who Are Also Evaluable by CA-125

Target Lesion ^a	Nontarget ^b	New Lesion	CA-125	Overall Best Response	Comments
CR	CR	No	Normal	CR	Best RECIST 1.1 response for CR and PR also requires it to be confirmed and maintained for at least 28 days if response is primary endpoint
CR	Non-CR Non-PD	No	Not PD	PR	
CR	CR	No	PR but not normal	PR	
CR	NE	No	PR	PR	
PR	Non-PD or NAE	No	Not PD	PR	
NAE	Non-PD	No	PR	PR	
PD or New	>28 days from CA-125 PR ^d	--	PR	PR	
SD ^c	Non-PD	No	PR	PR	
SD ^c	Non-PD or NAE	No	Not PR and not PD	SD	
PD or New	≤28 days from CA-125 PR ^d	--	PR	PD	
PD	Any	Yes or No	Any	PD	
Any	PD	Yes or No	Any	PD	
Any	Any	Yes	Any	PD	
Any	Any	Yes or No	PD	PD	

^a Target lesions include up to 5 measurable lesions (2 per organ) as defined by RECIST 1.1.

^b Nontarget lesions include ascites and peritoneal thickening which are not measurable according to RECIST 1.1.

^c The protocol should specify the minimum time interval between 2 measurements for classification as stable disease.

^d Patients who have CA-125 response that occurs more than 28 days from PD according to RECIST 1.1 are considered a PR, according to best response, but PD if the RECIST 1.1 PD is within 28 days of CA-125 response. CR-complete response; PD-progressive disease; PR-partial response; SD-stable disease; NE-not evaluable; NAE-not all evaluated

Appendix 15: Glutathione (GSH), N-Acetylcysteine (NAC), or S-Adenosylmethionine (SAM)-Containing Products (Representative List) Glutathione (GSH)		N-acetylcysteine (NAC)		S-adenosylmethionine (SAM)	

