**Table 4-1 CA-125 Disease Response**

Response Category	Criteria	Additional information
Complete Response	50% reduction in CA-125 levels from a pretreatment sample. The value must also return to within normal range and be maintained for 28 days (i.e. <10% change between response and confirmation sample)	To have a response, the pre-treatment sample must be at least twice the upper limit normal range (ULN). The date when the CA-125 level is first reduced by 50% is the date of the CA-125 response.
Partial Response	50% reduction in CA-125 levels from a pretreatment sample that is maintained for 28 days, but result is not yet within normal range.	For a partial response, the CA-125 is not yet within normal range, the pre-treatment sample must be at least twice the ULN.
Normalized	CA-125 returned to within normal range, but was not twice the ULN at baseline	
Disease Progression	
Any of the following scenarios are categorized as PD.
 
For patients with CA-125 elevated at baseline:
 
 
- If CA-125 normalized (within normal range) at any point, then increases to twice ULN on 2 occasions at least 1 week apart, date of PD is when CA-125 was first measured at twice ULN.
 
- If CA-125 never normalizes (within normal range), then increases to twice the nadir value on 2 occasions at least 1 week apart, date of PD is when CA-125 was first measured at twice the nadir value.
 
 
For patients with normal CA-125 at baseline:
 
 
- If CA-125 increases to twice ULN on 2 occasions at least 1 week apart, date of PD is when CA-125 was first measured at twice ULN.
 
	
Non-PR/ Non-PD	None of the above are true	

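### The SAP's CA-125 and GCIG tables disagree with the protocol appendices they cite: a complete CA-125 responder with stable lesions is not graded PR although a partial one is, and other responders may match no row

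*SAP*

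**What the plan says.** SAP 4.3.4 takes the GCIG response rules from Table 4-1 and from Protocol Appendices 12 to 14. It uses Table 4-2 for patients without measurable disease at baseline and Table 4-3 for those with it.

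**SAP Table 4-1.** A CA-125 complete response needs a 50% fall, and "The value must also return to within normal range and be maintained for 28 days", glossed as "i.e. <10% change between response and confirmation sample". A partial response is a "50% reduction in CA-125 levels from a pretreatment sample that is maintained for 28 days, but result is not yet within normal range". The last category, Non-PR/Non-PD, is residual: "None of the above are true".

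**SAP Table 4-3.** It refers to Table 4-1 for its CA-125 definitions. With stable target lesions and non-target lesions not progressing, a CA-125 PR gives an overall PR, and a CA-125 that is neither PR nor PD gives SD. Two rows that lead to PR (target PR; target CR with non-target non-CR/non-PD) require a CA-125 that is Not PD. Footnote [2] says this term "includes Normalized, CR, or PR".

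**Protocol.** Appendix 12 defines a CA-125 response as a fall of at least 50%, confirmed and held for 28 days, with no condition that the value stay above normal. Complete responders are those responders who also reach the reference range. On confirmation it says: "Intervening samples and the 28-day confirmatory sample must be less than or equal to (within an assay variability of 10%) the previous sample", and "Variations within the reference range of CA-125 levels will not interfere with the response definition". Table 10 (Appendix 14) uses "PR but not normal" in the row for target CR with non-target CR. Elsewhere it uses plain PR, or Not PD without restriction.

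**The concern.** A better marker response should not produce a worse overall grade. The SAP's definitions allow this because Table 4-1 splits CA-125 CR from PR, while several rows of Tables 4-2 and 4-3 still name only PR. In the protocol, PR covers every CA-125 response; its qualifier about not being normal would otherwise be pointless.

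Two further wordings point the same way. Footnote [2] leaves out the residual marker category, and the 10% gloss is two-sided where Appendix 12 bars only rises.

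At stake are the ovarian cohort's GCIG ORR and duration of response in Parts 1 and 2, and GCIG DCR where a patient gets no grade. With two named sources that disagree, the grade would depend on which one the programmer follows.

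**Working it through.** This is a check of classification logic; the plan states no figure to reproduce. The rows of SAP Tables 4-2 and 4-3 and of Protocol Tables 9 and 10 were set out as look-ups and compared with no new lesions. The two rows that depend on the 28-day interval were left out.

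**1. CA-125 CR and PR.** Results for patients with measurable disease, taking footnote [2] as a full list:

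| Target / non-target | CA-125 | SAP Table 4-3 | Protocol Table 10 |
|---|---|---|---|
| SD / CR or non-CR/non-PD | PR | PR | PR |
| SD / CR or non-CR/non-PD | CR | SD | PR |
| PR / CR or non-CR/non-PD | Non-PR/Non-PD | no row | PR |
| CR / non-CR/non-PD | Non-PR/Non-PD | no row | PR |
| CR / CR | Non-PR/Non-PD | no row | no row |

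**2. Count.** 3 target grades (CR, PR, SD) × 2 non-target states × 4 non-PD marker categories = 24 combinations.

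- SAP as written, footnote [2] exhaustive: 2 are SD instead of PR and 3 have no row instead of PR, so 5 of 24 differ.
- Footnote [2] illustrative: the 3 close and 2 of 24 still differ.
- Footnote [2] exhaustive and the SD row's marker condition read only as the residual category of Table 4-1: the 2 become no row, and Normalized with stable lesions (SD in the protocol) also loses its row in 2 cells. That makes 3 + 2 + 2 = 7 of 24.

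No reading that keeps Table 4-1's split gives PR to a CA-125 CR with stable lesions.

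**3. Outside the 24.**

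- Table 4-2: CA-125 CR with non-CR/non-PD lesions matches no row; Protocol Table 9 gives PR.
- Table 4-3: the marker entries for target CR/non-target CR and target CR/non-target not evaluable are swapped relative to Protocol Table 10. As a result, target CR/not evaluable with CA-125 CR has no row; the protocol gives PR.
- Table 4-3: target not all evaluated with non-PD lesions and CA-125 CR has no row; the protocol gives PR.

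**4. The 10% gloss.** An illustration with assumed values: ULN 35, baseline 400, then 30, then 20 at confirmation.

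- Fall from baseline: (400 − 30)/400 = 92.5%. Baseline exceeds 2 × 35 = 70.
- Change to confirmation: (30 − 20)/30 = 33%, so CR fails on the literal 10% limit.
- PR fails because the value is normal. Normalized fails because the baseline was at least twice ULN. PD does not apply. The result is Non-PR/Non-PD.
- Appendix 12: 20 is below 30 and both are within range, so the patient is a complete responder.

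**5. Size per patient.** Protocol 3.2 plans about 21 evaluable patients in Part 1 Cohort A and 16 per Part 2 schedule: 1/21 = 4.8 points and 1/16 = 6.25 points of ORR.

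**The case against.** The strongest reply is that SAP 4.3.4 itself names Appendices 12 to 14, which give the expected grades, so no wrong result is certain. This stands in part. The accurate description is a conflict between two named derivations, and the SAP does not say which prevails. The readable text of SAP Section 5 lists no intended change to the CA-125 rules.

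For footnote [2], the verb in "includes Normalized, CR, or PR" can be read as illustrative, and a category called Non-PR/Non-PD is plainly not PD. The marker [2] also sits on the target CR row rather than the target PR row. On that reading this gap closes, so it is conditional. For the 10% gloss, Appendix 12 rescues the example if it is applied; the defect lies in the literal wording.

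Three stronger inferences are tempting and not supported:

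- *That about a fifth of patients would be misgraded.* The 5 of 24 are table cells, and the documents give no frequencies.
- *That unmatched responders would be dropped.* The SAP does not say how an unmatched patient is handled.
- *That a GCIG ORR below the RECIST ORR would reveal the error.* Protocol Table 10 itself grades CA-125 PD as PD, and SAP 2.1 uses different populations for the two rates.

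**Conclusion.** Wrong as written. The firm part is that a CA-125 complete responder with stable lesions gets SD or no row in Table 4-3, where Protocol Appendix 12 and Table 10 give PR; the matching gap in Table 4-2 is equally firm. The footnote gap holds if the list is exhaustive, and the 10% problem holds if the gloss is applied literally without Appendix 12.

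The scope is limited. The primary DCR uses RECIST 1.1 and is untouched, and SAP 3.2 confines formal testing to the primary endpoint. What can move is descriptive: GCIG ORR and duration of response in ovarian patients, and GCIG DCR where no row matches. DCR is less sensitive to SD in place of PR because SD of at least 12 weeks counts as control.

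The 4.8 and 6.25 points per patient use planned sizes as denominators. The actual denominator is the GCIG Evaluable Population, whose size the documents do not give, and the number of affected patients is unknown.

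**What to change.** **Table 4-3**

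- (a) Restore Protocol Table 10's entries: target CR/non-target CR takes a CA-125 PR that is not normal; target CR/non-target not evaluable takes any CA-125 response (CR or PR).
- (b) Replace PR by CA-125 response (CR or PR) in the row for target lesions not all evaluated, the SD-to-PR row and the two 28-day rows.
- (c) Make the SD-to-SD row require no CA-125 response (neither CR nor PR) and no CA-125 PD. Without this, a CA-125 CR would match both the PR and the SD row.
- (d) Make footnote [2] cover every category except PD, naming Non-PR/Non-PD.

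**Table 4-1.** Replace the 10% gloss by: confirmatory sample not more than 10% above the previous sample, with variation inside the reference range ignored.

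**Table 4-2.** Let row 2 cover CR or PR where the CR row is not met.

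Some combinations have no row in Protocol Table 10 either, such as target CR/non-target CR with a Non-PR/Non-PD marker. Change (c) also leaves stable target lesions with non-target lesions not all evaluated and a CA-125 CR without a row, as both documents already do for a CA-125 PR. The SAP should state how unmatched patients are graded.

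The cost is wording in three SAP tables and re-programming one derivation. No new data are needed.

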#### 4.3.5. EORTC QLQ Scoring

The EORTC QLQ assessments will be scored according to the EORTC QLQ-C30 Scoring Manual, as described below.

##### Raw Score:

For all scales, the Raw Score (RS) is the mean of the component items, where I = Item:

- Raw Score:  $RS = (I_1 + I_2 + \dots + I_n)/n$

The items for each scale are identified in Table 4-4, Table 4-5, Table 4-6, and Table 4-7.

Transformed Score:

For each domain, the linear transformation is as follows:

- Functional scales:  $Score = \{1 - ((RS - 1)/range)\} * 100$
- Symptom scales / items and Global health status / QoL:  $Score = \{(RS - 1)/range\} * 100$

Range is the difference between the maximum possible value of RS and the minimum possible value. Most items are scored 1 to 4, giving range = 3. The exceptions are the items contributing to the global health status / QoL, which are 7-point questions with range = 6, and the initial yes/no items on the earlier versions of the QLQ-C30 which have range = 1.

Example: Emotional Functioning:  $RS = (Q21+Q22+Q23+Q24)/4$

$$EF \text{ Score} = \{1 - (RS-1)/3\} * 100$$

Missing Scores:

If less than half of the scores are missing for any domain, the remaining items will be used applying the standard equations given above for calculating the scale scores. If at least half of the scores are missing, the scale will be missing. For single item measures, the score will be missing.

Example: Q23 is missing

Emotional Functioning:  $RS = (Q21+Q22+Q24)/3$

$$EF \text{ Score} = \{1 - (RS-1)/3\} * 100$$

**Table 4-4 EORTC QLQ-C30 Scoring – General Questions**

Domain	Scale		Number of Items	Item Range*	Version 3.0 Item Numbers
Global health status	Global health status /QoL	QL2	2	6	29, 30
Functioning Scales	Physical functioning	PF2	5	3	1 to 5
	Role functioning	RF2	2	3	6, 7
	Emotional functioning	EF	4	3	21 to 24
	Cognitive functioning	CF	2	3	20, 25
	Social functioning	SF	2	3	26, 27
Symptom scales/items	Fatigue	FA	3	3	10, 12, 18
	Nausea and vomiting	NV	2	3	14, 15
	Pain	PA	2	3	9, 19
	Dyspnoea	DY	1	3	8
	Insomnia	SL	1	3	11
	Appetite loss	AP	1	3	13
	Constipation	CO	1	3	16
	Diarrhoea	DI	1	3	17
	Financial difficulties	FI	1	3	28

\* Item range is the difference between the possible maximum and the minimum response to individual items; most items take values from 1 to 4, giving range = 3.

**Table 4-5 EORTC QLQ-OV28 Scoring - Ovarian Cancer Supplement**

Domain	Scale	Number of Items	Item Range*	Version 3.0 Item Numbers
Symptom scales/items	Abdominal/GI	6	3	1 to 6 (31 to 36 in eCRF)
	Peripheral neuropathy	2	3	11, 12 (41, 42)
	Hormonal	2	3	18, 19 (48, 49)
	Body image	2	3	20, 21 (50, 51)
	Attitude to disease/treatment	3	3	22 to 24 (52 to 54)
	Chemotherapy side effects	5	3	13 to 17 (43 to 47)
	Other single items	4	3	7 to 10 (37 to 40)
	Sexuality**			25 to 28 (55 to 58)

\* Item range is the difference between the possible maximum and the minimum response to individual items; most items take values from 1 to 4, giving range = 3.

\*\* The scaling performance of items 25-28 has yet to be established.

**Table 4-6 EORTC QLQ-CX24 Scoring - Cervical Cancer Supplement**

Domain	Scale		Number of Items	Item Range*	Version 3.0 Item Numbers
Functional Scales	Body image	CXBI	3	3	15-17 (45-47 in eCRF)
	Sexual activity	CXSXA	1	3	19 (49)
	Sexual enjoyment	CXSXE	1	3	24 (54)
	Sexual/vaginal functioning	CXSV	4		20-23 (50-53)
Symptom scales	Symptom experience	CXSE	11	3	1-7, 9, 11-13 (31-37, 39, 41-43)
	Lymphoedema	CXLY	1	3	8 (38)
	Peripheral neuropathy	CXPN	1	3	10 (40)
	Menopausal symptoms	CXMS	1	3	14 (44)
	Sexual worry	CXSW	1	3	18 (48)

\* Item range is the difference between the possible maximum and the minimum response to individual items; most items take values from 1 to 4, giving range = 3.

**Table 4-7 EORTC QLQ-EN24 Scoring - Endometrial Cancer Supplement**

Domain	Scale		Number of Items	Item Range*	Version 3.0 Item Numbers
Functional Scales	Sexual interest	ENSXI	1	3	49
	Sexual activity	ENSXA	1	3	50
	Sexual enjoyment	ENSXE	1	3	54
Symptom scales	Lymphoedema	ENLY	2	3	31-32
	Urological symptoms	ENUR	4	3	34-37
	Gastrointestinal symptoms	ENGI	5	3	38-42
	Poor body image	ENBI	2	3	47-48
	Sexual/vaginal problems	ENSXV	3	3	51-53
	Pain in back and pelvis	ENBP	1	3	33
	Tingling/numbness	ENTN	1	3	43
	Muscular pain	ENMP	1	3	44
	Hair loss	ENHL	1	3	45
Taste change	ENTC	1	3	46	

\* Item range is the difference between the possible maximum and the minimum response to individual items; most items take values from 1 to 4, giving range = 3.

CCI

Relevant Output

CCI

## 4.5. Safety Analyses

Safety analyses will be conducted using the safety population.

### 4.5.1. Study Drug Exposure

Study drug exposure will be determined by duration, percent compliance, total drug taken, and dose intensity, as described below.

Duration of study drug exposure will be calculated as the number of day patients were administered study drug, as determined below, and will be summarized by cohort using descriptive statistics. Duration of study drug exposure for each patient will also be provided in a data listing, along with number of cycles administered.

$$\text{Duration of Study Drug Exposure} = (\text{Date of last dose} - \text{Date of first dose}) + 1$$

Percent compliance will be summarized for each patient from date of first dose through the treatment period per the following definition:

$$\text{Percent Compliance} = \frac{\text{Amount of drug taken (mg)}}{\text{Amount of drug prescribed (mg)}} \times 100$$

Patient compliance with study drug will be summarized by cohort and presented in a by-patient data listing. Percent compliance will be summarized separately for patients who completed the study versus those who withdrew early (i.e. patient decided to discontinue study treatment, patient withdrew consent, or patient was withdrawn from treatment due to protocol violation) so as to distinguish between those patients who were compliant throughout the entirety of the study versus those who were compliant until they withdrew. In the listing, patients who withdrew from the study early will be flagged.

Total drug taken will be presented in mg, and calculated by a summation of all doses received. Total drug prescribed will be presented in mg, and calculated by a summation of all doses prescribed. For patients receiving a mg/m^2 dose, amount of drug prescribed will be calculated using baseline BSA calculated using the Dubois and Dubois formula listed in Section 4.2 (Dubois and Dubois, 1916).

Dose intensity (defined as total drug taken divided by duration of exposure, presented in mg/day and mg/week), number of missed doses, number of dose interruptions, duration of dose interruption, number of dose reductions, and number of dose escalations will also be summarized. Duration of dose interruption will be calculated as the number of days from the most recent dose prior to the interruption until the next dose received.

Dosing information for each patient will be presented in a data listing.

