3.1.1 Definition of Treatment Cycle and Duration

Each cycle is 28 days (4 weeks) long. In twice-weekly dose schedules (i.e., Part 1 and Part 2, Schedule 1), 8 doses of selinexor will be administered per cycle. In the once-weekly dose schedule (i.e., Part 2 Schedule 2), 4 doses of selinexor will be administered per cycle. Twice-weekly doses of selinexor must be administered at least 36 hours apart; once weekly doses of selinexor must be administered at least 5 days apart.

Dose escalations and reductions/interruptions are permitted according to safety guidelines in this protocol or in consultation with a sponsor representative (see Section 6.3).

Dose schedules in Parts 1 and 2 are as follows:

- **Part 1:** Patients will receive oral selinexor 50 mg/m² twice weekly (e.g., Monday and Wednesday, Tuesday and Thursday, Wednesday and Friday or Thursday and Saturday) in each week of a 4-week cycle.

- **Part 2:**
 - *Schedule 1* – Patients will receive oral selinexor 35 mg/m² twice weekly (e.g., Monday and Wednesday, Tuesday and Thursday, Wednesday and Friday or Thursday and Saturday) in each week of a 4-week cycle.
 - *Schedule 2* – Patients will receive oral selinexor 50 mg/m² once weekly in each week of a 4-week cycle (e.g., Monday of each week).

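### Dose intensity stops the clock on the day of the last dose, so it overstates weekly dose by an amount that depends on schedule and time on treatment

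*SAP*

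**What the plan says.** SAP Section 4.5.1 gives the measure as "Dose intensity (defined as total drug taken divided by duration of exposure, presented in mg/day and mg/week"). For the numerator, "Total drug taken will be presented in mg, and calculated by a summation of all doses received". The denominator is a calendar span, last dose date minus first dose date plus one day, although the text introduces it differently: "Duration of study drug exposure will be calculated as the number of day patients were administered study drug".

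Protocol Section 3.1.1 sets the two Part 2 regimens. Schedule 1 is 35 mg/m2 twice weekly, with example day pairs that are always two days apart; "In twice-weekly dose schedules (i.e., Part 1 and Part 2, Schedule 1), 8 doses of selinexor will be administered per cycle". Schedule 2 is 50 mg/m2 "once weekly in each week of a 4-week cycle (e.g., Monday of each week"), which makes 4 doses per cycle. SAP Section 3.2 presents Part 2 data by schedule, and SAP Section 3.8 gives the purpose of Part 2 as a once-weekly versus twice-weekly evaluation. No readable part of either document adds back the final dosing interval or plans a relative dose intensity; the exposure table shells are redacted.

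**The concern.** A weekly dose rate should count the time that each dose covers. Here the last dose contributes its milligrams but only one day. The missing days are a fixed number per patient, so the inflation is large for short courses and fades with time. The number also differs between once-weekly and twice-weekly dosing.

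Part 2 places these two schedules side by side with about 16 patients each (Protocol Section 3.2), and a reader will use delivered dose per week to interpret the efficacy and tolerability results. Exposure is summarised in the safety population, which includes anyone who took any study drug (SAP Sections 2.1 and 4.5), and the mean is among the statistics reported. Those who stop soonest would appear to be the most intensively dosed.

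**Working it through.** **Inputs.** Regimens from Protocol Section 3.1.1; day 1 and day 3 dosing from Protocol Table 2 and the example day pairs; formula from SAP Section 4.5.1. The SAP reports mg rather than mg/m2. The percentage overstatement is the same in either unit and, at equal body surface area, so is the ratio.

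**Planned dose.** Schedule 1: 35 × 2 = 70 mg/m2/week and 35 × 8 = 280 per cycle. Schedule 2: 50 × 1 = 50 and 50 × 4 = 200. These match the figures in the Protocol's summary of changes from Version 2.0 to 3.0. Planned ratio 70/50 = 1.40; difference 20.

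**SAP formula after n complete weeks, every dose taken.** The last dose falls on day 7n − 4 (Schedule 1) or day 7n − 6 (Schedule 2), so weekly intensity is

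- Schedule 1: 70n × 7/(7n − 4)
- Schedule 2: 50n × 7/(7n − 6)

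| Weeks | Schedule 1 | Schedule 2 | Ratio | Difference |
|---|---|---|---|---|
| 1 | 70/3 × 7 = 163.3 (+133%) | 50/1 × 7 = 350.0 (+600%) | 0.47 | −186.7 |
| 4 | 280/24 × 7 = 81.7 (+16.7%) | 200/22 × 7 = 63.6 (+27.3%) | 1.28 | 18.0 |
| 6 | 420/38 × 7 = 77.4 (+10.5%) | 300/36 × 7 = 58.3 (+16.7%) | 1.33 | 19.0 |
| 12 | 840/80 × 7 = 73.5 (+5.0%) | 600/78 × 7 = 53.8 (+7.7%) | 1.37 | 19.7 |
| 24 | 1680/164 × 7 = 71.7 (+2.4%) | 1200/162 × 7 = 51.9 (+3.7%) | 1.38 | 19.9 |

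**Unequal time on treatment.** With n1 weeks in Schedule 1 and n2 in Schedule 2, the ratio is 1.40 × [7n1/(7n1 − 4)] / [7n2/(7n2 − 6)]. It equals 1.40 when 4/n1 = 6/n2, that is, when n2 = 1.5 × n1. So 4 v 6 weeks gives 1.40, 4 v 8 weeks gives 1.46, and 12 v 6 weeks gives 1.26.

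**Effect on a small-arm mean (hypothetical).** Fifteen Schedule 2 patients fully dosed for 12 weeks plus one who stops after a single dose: (15 × 53.85 + 350)/16 = 72.4, against 50 planned and close to the 73.5 of fully dosed Schedule 1 patients. The median would remain 53.8.

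**Check of the repair.** End the denominator on the day before the next dose is due.

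- Schedule 2, 4 weeks: 22 − 1 + 7 = 28 days; 200/28 × 7 = 50. Single dose: 50/7 × 7 = 50.
- Schedule 1, 4 weeks, last dose the second of the week: 24 − 1 + 5 = 28 days; 280/28 × 7 = 70.
- Schedule 1, stopping after the first dose of week 4: 22 − 1 + 2 = 23 days; 245/23 × 7 = 74.6, against 245/22 × 7 = 78.0 under the SAP. The same stop in week 12 gives 805/79 × 7 = 71.3.

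**The case against.** A reader might infer that the formula always shrinks the contrast between the Part 2 arms. The documents do not support that. Time on treatment is an outcome, not a design constant, and the working shows that the ratio can be reduced, unchanged or inflated. Shrinkage is a statement about similar treatment lengths only.

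A reader might also infer that compliant patients will be reported above 100% of plan, or that delivered dose as a whole is misstated. The readable SAP expresses intensity in mg/day and mg/week, not as a percentage of plan. Its taken-versus-prescribed measure is percent compliance, which has no time denominator and is correct for this purpose. Total drug taken, missed doses, interruptions, reductions and escalations are summarised too.

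The effect is modest for longer courses, and permitted dose changes move the ratio further. If both arms escalate (Protocol Section 6.3.1), the planned ratio is 100/60 = 1.67, and a Schedule 1 patient reduced one level moves to once-weekly dosing (Protocol Table 3). Formal testing is confined to the primary endpoint (SAP Section 3.2). All of this stands, and it limits the importance of the point.

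The obvious repair, running to the end of the last dosing week, has a bias of its own. A Schedule 1 patient who stops after the first dose of week 4 with every due dose taken would show 245/28 × 7 = 61.25 against 70. That objection also stands, so the fix below uses the next due date instead.

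What does not stand is treating the formula as a neutral, disclosed choice. A rate that gives 350 mg/m2/week for one 50 mg/m2 weekly dose does not measure delivered weekly dose.

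**Conclusion.** The point holds in limited form. The SAP formula overstates weekly dose intensity in every schedule, by an amount that depends on dosing frequency and time on treatment. With full dosing and equal time on treatment, the Part 2 ratio is 1.28 at 4 weeks and 1.37 at 12 weeks instead of 1.40. With unequal time on treatment, the direction of the distortion cannot be known in advance. Single-dose and other very early stoppers give extreme values that can dominate a mean over about 16 patients. Beyond about 12 weeks the effect is small.

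These figures assume all doses taken at the starting dose, day 1/day 3 dosing in Schedule 1 with the last dose the second of its week, and equal body surface area between arms. The differential between schedules concerns Part 2; Part 1 starts all patients on twice-weekly dosing. Dose intensity is descriptive, so no conclusion about DCR, adverse events or percent compliance changes. The change is worth making because it affects how the schedule comparison is read and uses data already collected.

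**What to change.** In SAP Section 4.5.1, for dose intensity only, run the denominator from the first dose to the day before the next dose would be due under the schedule in force at the last dose:

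- once weekly: last − first + 7 days;
- twice weekly on a day 1/day 3 pattern: last − first + 2 days if the last dose was the first of its week, + 5 days if it was the second.

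Also report intensity relative to the doses prescribed for that same period, so that permitted escalations and reductions are reflected.

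Keep the duration-of-exposure formula, but reword its introduction so that it describes a calendar span from first to last dose rather than days on which drug was administered.

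The cost is one formula and one sentence, with no new data. Reported intensity becomes slightly lower for most patients and much lower for very early stoppers. A residual overstatement remains for a twice-weekly patient who stops after the first dose of a week: small in later weeks (74.6 v 70 in week 4, 71.3 in week 12), but still 35/2 × 7 = 122.5 after a single dose, against 245 now. Time during which doses are held after the last dose taken, before treatment is formally stopped, stays outside the denominator apart from that final interval; a footnote should say so.
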